## Justification and Feasibility

Dental plaque is a significant factor in oral health, with implications for systemic health. Dental plaque is a complex biofilm found on tooth surfaces, and plaque accumulation is enhanced by bacterial aggregation between and among species. Microbial flora are concentrated in dental plaque, which is a complex environmental niche of interdependent microorganisms embedded in bacterial and salivary products.

Accumulation of dental plaque is closely associated with oral inflammation, including gingivitis and periodontitis. The standard clinical experimental model for gingivitis involves holding of tooth brushing to induce or exacerbate the disease. In healthy adult subjects who withheld tooth brushing, Scott and colleagues found a progressive, positively correlated increase in dental plaque and GCF biomarkers over the 21 day study period; when inflammation was assessed again after 7 days of brushing resumption, it had resolved. Further, they found that GCF IL-1 $\beta$  increased after 3 days of plaque accumulation, in advance of clinical signs of inflammation. When measured over shorter intervals in a briefer study (tooth brushing withheld for 3 days), Zhang and colleagues found that GCF IL-1 $\beta$  elevated after one day, and returned to baseline within 2 days of resumption of brushing.

Oral mucosal inflammation, and in particular gingivitis or periodontal disease, provides opportunities for bacterial overgrowth, and richly vascularized and inflamed tissues associated with these diseases are susceptible to bacterial invasion. Gingivitis and periodontitis are known to increase the risk of bacteremia related to invasive dental procedures in healthy populations. Paradoxically, tooth brushing has also been linked to transient bacteremia in healthy subjects. In critically ill adults, central line catheters are the predominant but not the sole source for bacteremia. The role of other sources, including tooth brushing, has not been elucidated.

The mucosal inflammatory response to dental plaque is complex, and in addition to immune stimulation by microbes within dental plaque, the response may also be triggered or exacerbated by non-microbial components of the biofilm. Tooth brushing is widely recognized as the optimal way to remove dental plaque and reduce the associated inflammatory response. Other oral care strategies, such as foam swabs, are not effective in removing dental plaque. Chlorhexidine suppresses microbial growth in dental plaque, but does not remove the physical biofilm.

In the absence of evidence regarding optimal frequency, tooth brushing practices vary. Current guidelines for care of mechanically ventilated adults do not have an evidence based tooth brushing component, and there is not a consensus in the literature regarding appropriate frequency of tooth brushing in the critically ill. The American Dental Association (ADA) recommends that healthy persons brush their teeth twice daily. In preliminary research prior to the R01, we compared usual care to an intervention performed by nurses every 12 hours in critically ill adults (both mechanically ventilated and not ventilated). In the previous funding period of the R01, tooth brushing was performed three times daily, based on our previous findings of prevalent xerostomia and dental plaque accumulation in mechanically ventilated adults. Three interventions per day is congruent with nursing care patterns of AM, PM, and HS administration for other routine nursing procedures such as back care. Other ICU research protocols, focused on VAP prevention, have included tooth brushing twice daily or three times daily. There are no published research reports of once daily tooth brushing in hospitalized patients, and there is considerable resistance among nurses to eliminating it entirely.

Surveys of nurses' practices reveal wide discrepancies in clinical practices among institutions and among individual nurses, and a lack of specificity in institutional protocols. In the absence of evidence regarding benefit and risk, many nurses have adopted a "more is better" approach to oral care. In our previous research, nurses indicated that they administered oral care as frequently as seven times per day, and clinical articles have inappropriately cited our previous publications as support for increased frequency for oral care. Evidence regarding the optimal frequency for tooth brushing is lacking, and is essential to informing nursing practice.

## Preliminary Studies

We have substantial experience which enhances the likelihood that we can successfully accomplish the specific aims. We have been active in research related to oral care in critically ill adults for over 2 decades. We have direct and extensive experience in enrolling critically ill subjects; delivering oral care interventions in intensive care settings, including tooth brushing intervention at the maximal frequency proposed; measuring dental plaque and global oral health; obtaining, measuring, and analyzing systemic and oral biomarker data; and quantifying HAIs. In two previous research studies, we quantified and characterized dental plaque accumulation in subjects who were not receiving a standardized oral care intervention. We have successfully completed multiple RCTs, and the data we have generated has had direct impact on clinical practice, including contributing to national guidelines for care of mechanically ventilated adults.

1. Oral Care in Mechanically Ventilated Adults (R01 NR007652, initial funding period). The primary aim of the initial funding period of this R01 was to test the effects of tooth brushing, CHX, and a combination oral care intervention (tooth brushing plus CHX) on dental plaque, oral microbial flora and oral immunity in critically ill mechanically ventilated adults. A secondary aim was to examine the effects of tooth brushing, CHX, and combination (tooth brushing

plus CHX) oral care interventions on development of VAP in critically ill mechanically ventilated adults. A between-subjects 2X2 factorial design was used; 547 subjects were randomly assigned to 1 of 4 treatments: 0.12% solution CHX oral swab twice daily, toothbrushing three times daily, both toothbrushing and CHX, or control (usual care). Oral care interventions were provided by study personnel. Dental plaque was scored on study days 1, 3, 5 and 7 using a standardized scale, the University of Mississippi Oral Hygiene Index (UM-OHI), with observations augmented by use of a dental plaque disclosing agent, visible only under ultra-violet (UV) light so that study personnel providing interventions and clinical providers were not aware of plaque assessment results. Plaque assessors were blinded to subject group assignment. Subjects remained in the study for a maximum of 7 days; participation ended with extubation. Subjects were 61% male, with a mean age of 47.9 years and mean APACHE III score of 77. Serial dental plaque data from admission to the study through day 3 were available for 222 subjects. Mixed model analysis of variance showed a significant effect on dental plaque of the toothbrushing intervention ( $p=0.0411$ ). The CHX intervention had no effect on the presence of dental plaque ( $p=0.9397$ ), and there was no interaction effect between toothbrushing and CHX.

In contrast, when we tested the effects of the interventions on VAP risk as measured by the Clinical Pulmonary Infection Score (CPIS), CHX significantly reduced the incidence of pneumonia on day 3 (CPIS  $\geq 6$ ) among patients who had CPIS  $< 6$  at baseline ( $P = .006$ ), while tooth brushing had no effect on CPIS ( $p = .54$ ) and did not enhance the effect of CHX. We reasoned that although both CHX and tooth brushing reduce organisms in dental plaque, CHX has bacteriocidal activity while tooth brushing mechanically reduces the number of organisms without residual activity on those remaining in the mouth. Thus, dental plaque remained physically present on the teeth of patients who received CHX, but organisms present in the plaque were inhibited. Although tooth brushing physically removed dental plaque, the intermittent reduction in organism numbers achieved by tooth brushing was insufficient to reduce risk of VAP.

This study provided a critical foundation for the proposed project. It provided us with extensive experience in delivering the tooth brushing intervention, conducting dental plaque assessments in mechanically ventilated adults, and interpreting oral health data. It provided important evidence that although tooth brushing 3 times a day did not reduce VAP risk, it did reduce dental plaque. While not statistically significant, the trend toward worse CPIS scores in subjects who received tooth brushing 3 times a day spurred our interest in establishing the optimal frequency for tooth brushing and in testing non-equivalence of less frequent (once daily) tooth brushing intervals.

2. Pilot Study of Oral Care in the Adult Intensive Care Unit. Prior to the initial funding period of this R01, we conducted a pilot study with primary aims to 1) describe the oral status of critically ill persons hospitalized in a medical respiratory intensive care unit, and 2) evaluate the effects of a defined oral care protocol on the oral health status of critically ill patients. A cohort, quasi-experimental, longitudinal (before/after) study design was used. Sixty critically ill subjects were included in the study, 30 in a control group (whose oral care was performed by the bedside nurse without knowledge of the oral care protocol) and 30 in an intervention group (after nurses had been educated about an oral care protocol). The study did not focus on mechanically ventilated patients, although mechanically ventilated subjects were included.

The oral care protocol included tooth brushing every 12 hours from the day of admission into the study through day 7. Data were collected on the date of admission to the study and on days 3, 5, and 7. Oral assessments, using 100 mm visual analog scales, were completed in the morning on admission to the study and on days 3, 5, and 7 by a dental hygienist and the bedside nurse. The intervention group mean inflammation scores (mean = 3.9 on scale of 0-10,  $SEM = 3.0$ ) were significantly lower ( $p = 0.0276$ ) than the control group (mean = 12.4 on scale of 0-10,  $SEM = 2.2$ ). Although not statistically significant when analyzed by *t*-test, the experimental group also had lower mean values than the control group on a visual analogue scale of plaque (14.2 vs. 18.3). Despite the measurement by visual analogue scale being less robust than methods in our subsequent studies, this very early study provided us with initial data suggesting that tooth brushing in critically ill patients could affect both mucosal inflammation and dental plaque.

3. Backrest Position and Oral Health: Effect on VAP (R15 NR04730, PI: [name], Co-I: [name]). This non-experimental, longitudinal study of 66 mechanically ventilated adults was conducted to describe 1) the relationship of backrest elevation on the development of VAP, and 2) the relationship of oral health status on the development of VAP. Assessment of oral health status on study days 1, 4, and 7 included biomarker measurement (salivary lactoferrin and IgA), DMFT, a visual analogue scale of dental plaque, and semi-quantitative oral and endotracheal aspirate cultures. Data were analyzed using a mixed linear model.

The analysis of specific aim 2 revealed complex relationships among severity of illness, dental plaque scores at baseline and on day 4, and CPIS at baseline and on day 4. Correlations were significant with day 4 CPIS for APACHE II ( $P=.007$ ), day 4 salivary volume ( $P=.02$ ), interaction of APACHE II score and day 1 CPIS ( $P<.001$ ), and interaction of day 1 CPIS and plaque ( $P=.01$ ). The model indicated that increased dental plaque was most predictive of pneumonia in patients with high APACHE scores and lower baseline CPIS. The number of organisms present in oral cultures increased

from Day 1 to Day 4, and remained high on Day 7. In addition to identification of non-pathogenic oral flora, we were successful in identifying potential VAP pathogens in oral cultures (including *S. aureus*, *P. aeruginosa*, and *A. baumanii* ) preceding or concurrent with their appearance in endotracheal aspirates. These results indicated that oral health of critically ill patients was often compromised at the time of intubation, and deteriorated over time. Additionally, this study provided our first opportunities to collect salivary and microbiological samples from critically ill adults, and to analyze salivary biomarkers.

**4. Dental Plaque Accumulation in Mechanically Ventilated Adults.** In a sub-study of this R01 during its initial funding period, dental plaque data was evaluated longitudinally in a subset of the control group enrolled within 24 hours of intubation in the first year of data collection of R01 NR007652 (n=137). Subjects in the control group received usual oral care delivered by the bedside nurse; nurses were free to individualize the method of oral care, and the study units did not have protocols that specified tools and solutions for oral care. Baseline oral health status was assessed by a count of decayed, missing, and filled teeth (DMFT). Dental plaque was assessed using the UM-OHI on study days 1, 3, 5 and 7; observations were augmented by use of a dental plaque disclosing agent, visible only under ultra-violet (UV) light. This dental plaque assessment strategy was substantially more valid and reliable than our previous VAS. On the day of intubation, subjects had greater than 73% mean dental plaque coverage of tooth surfaces, and mean dental plaque remained greater than 60% through day 7, with statistical differences only between day 1 and day 7 ( $p = .03$ ). We further examined the pattern of dental plaque accumulation by location (buccal or lingual) and by tooth type (molars, premolars, canines, incisors). Dental plaque averages for the buccal (67%) and lingual (68%) surfaces were equivalent. The molars and premolar tooth types had the most dental plaque (greater than 70%) when compared to the other tooth types. These data reinforced earlier preliminary results regarding preexisting oral problems in mechanically ventilated adults, and further quantified high levels of dental plaque and DMFT scores. Further, the data indicated that usual oral care provided by bedside nurses was not effective in plaque removal.

**5. Comparison of biomarkers in blood and saliva.** The objective of this study, funded by the current project and a VCU HHMI Science Education Project in Systems Biology Summer Scholar Award (to [name]), was to compare multiple biomarkers (27 cytokines) in plasma samples, passive drool saliva samples, and filter paper saliva samples in 50 healthy adults. Demographic data and three samples were obtained from each subject: saliva collected on filter paper over 1 minute, saliva collected by passive drool over 30 seconds, and venous blood (3 mL) collected by venipuncture. The 27 cytokines selected were bundled together in the commercially available cytokine multiplex assay, reflect both pro-and anti-inflammatory immune response, and are commonly used as a panel in assessment of immune function. Assays were conducted using Bio-Rad multiplex suspension array technology. Descriptive statistics and pairwise correlations were used for data analysis. The sample was 52% male and 74% white. Mean age was 26 (range= 9–63 years,  $sd = 9.7$ ). The most consistent and highest correlations were between the passive drool and filter paper saliva samples. Between passive drool and filter paper saliva samples, statistically significant correlations were found among 16 of the 27 tested cytokines, including IL-1 $\beta$ , IL-1ra, IL-4, IL-7, IL-8, IL-9, IL-10, IL-12, IL-13, IL-15, G-CSF, IFN- $\gamma$ , IP-10, MCP-1, MIP-1 $\beta$ , and VEGF. Because the oral cavity represents a distinct environmental niche, and immune biomarkers are influenced by processes of local immunity, we predicted that salivary values would differ from plasma values, and we were correct. Between plasma and passive drool saliva samples, only 3 cytokines were statistically significantly correlated (IL-6, IFN- $\gamma$ , and MIP-1 $\beta$ ). This small descriptive correlational study in healthy adults is important because it demonstrates our ability to use a filter paper method for collection and analysis of oral biomarkers, as we will do with GCF IL-1 $\beta$  in the proposed project.

**6. Risk Reduction: Oral Care, Bacteremia, and Critical Care.** In a companion project to the initial R01 funding period (F31 NR009596, Fellow: [name]), the goals were to determine (1) the incidence of transient bacteremia related to tooth brushing in mechanically ventilated critically ill adults; (2) the relationship of oral microbial cultures and dental plaque scores to the incidence of transient bacteremia, clinical outcomes, and indicators of infection; and (3) the relationships among patient characteristics and clinical outcomes. All subjects (n=30) received a tooth brushing intervention twice daily for up to 48 hours. Three blood samples (before tooth brushing, 1 minute after the tooth brushing intervention, and 30 minutes after the intervention) for quantitative culture (lysis filtration) were collected at the first and last scheduled interventions. Five subjects (17%) had positive oral cultures for organisms other than normal oral flora (including *S. pneumoniae*, *coagulase-negative Staphylococcus*, *E. coli*, *S. aureus*, and *P. aeruginosa*) before the first tooth brushing intervention. None of the 30 subjects had evidence of transient bacteremia by positive quantitative blood cultures before or after the tooth brushing interventions. Patient characteristics were not statistically significant predictors for systemic inflammatory response syndrome, length of hospital stay, or length of intubation. In this small sample, dental plaque, DMFT and APACHE score were not found by logistic regression to be independent predictors of SIRS (likelihood ratio chi-square = .79,  $P = .85$ ). Despite the small sample size and limited length of data collection, this project provided

the opportunity to explore tooth brushing risk factors which we will further investigate in the proposed larger project, with a longer planned intervention period and post-extubation follow up.

Taken together, the preliminary studies presented in this application provide a substantial foundation for the proposed work, and clearly point to the examination of the frequency of tooth brushing as the final critical step in developing the evidence base for oral care in mechanically ventilated patients. Further, the preliminary studies document our expertise in the content relevant to and methodologies of the proposed project.

## IX. RESEARCH DESIGN AND METHODS

### Design

We will use a prospective, randomized, experimental design to accomplish the specific aims. Subjects (n=345) will be randomly assigned within 36 hours of intubation to one of three intervention groups which differ in frequency of tooth brushing (once, twice, or three times daily). The intervention, a standardized tooth brushing protocol developed and tested in the previous project, will be delivered by study personnel. Subjects will continue to receive scheduled interventions for the first 7 days of intubation, or until extubated if extubation occurs within 7 days; for subjects extubated within the intervention period, data collection will continue on days 1, 3, and 5 post-extubation. Dental plaque assessment, GCF for IL-1 $\beta$  determination, and data regarding HAIs and clinical status (for example, severity of illness) will be collected daily by study personnel who are blinded to group assignment.

All subjects will receive standard clinical care for mechanically ventilated patients, as per clinical guidelines and clinical agency guidelines. Standard clinical care includes all components of the IHI ventilator care bundle, including daily CHX. All subjects will receive oral comfort care by clinical providers at the provider's discretion. We will monitor reported compliance with the ventilator care bundle, and record characteristics and frequency of oral comfort care provided in order to assure that groups do not differ in usual clinical care.

**Sample.** The sample of 345 subjects will be drawn from all patients over the age of 18 years admitted to the Intensive Care Units at TGH who have been intubated less than 36 hours and are being mechanically ventilated. Both male and female subjects from all ethnic and racial backgrounds will be recruited. Subjects will be randomized to group according to a permuted block design developed by [name] such that after every  $k$  subjects balance will be maintained between the groups. For inclusion, subjects must be within 36 hours of initial intubation, have at least one tooth (to permit plaque assessment and GCF collection), and they or their legally authorized representative (LAR) must be able to provide informed consent in English or Spanish. Exclusion criteria include anticipation by the clinical provider of imminent patient death, or medical contraindication to tooth brushing (for example, unstable facial fractures). In order to fully enroll the study during the requested 4 year funding period, we will target enrollment of 10 subjects per month; in the current project, we exceeded this monthly target in our TGH sample.

**Setting.** Subject recruitment, enrollment, and interventions will be conducted at Tampa General Hospital (TGH) in Tampa, Florida. As one of the largest hospitals in Florida, TGH is licensed for 1,004 beds. Approximately 73.6% of admissions are white, 20.7% are African-American, and 17.2% are Hispanic. TGH is the area's only level I trauma center and one of just four burn centers in Florida. In the current project, we have established excellent research relationships and been successful in meeting target enrollments. [name] (Project Director) is credentialed by the TGH Office of Clinical Research.

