Recruitment and enrollment. All patients admitted to the Intensive Care Units at TGH who are intubated will be assessed for possible inclusion in the study. The PI, co-investigators, Project Director or GRAs will make daily rounds to the adult ICUs and ask the charge nurse to identify any patients, by room number, that have been intubated within the last 36 hours. A HIPAA waiver for screening and recruitment is requested for this study to allow the study staff to review the medical records for screening and recruitment purposes. If a patient meets study criteria (age 18 or older, within 36 hours of initial intubation, have at least one tooth, and they or their legally authorized representative able to provide informed consent in English or Spanish) and has no exclusions (anticipation by the clinical provider of imminent patient death, or medical contraindication to tooth brushing), the potential subject will be approached for a discussion about willingness to participate. If the subject is unable to provide consent due to sedation or inability to communicate, the legally authorized representative (LAR) will be approached, the study will be reviewed and permission for the subject to participate will be obtained from the LAR; in these cases, we will attempt to obtain assent of the subject as well, and will make additional attempts to consent the subject directly as their condition improves. In our experience, potential subjects who are critically ill, especially during the first 36 hours of intubation, are always sedated to some degree, and their ability to communicate effectively is compromised by endotracheal intubation; for these reasons, permission for the subject's participation has generally been obtained from the LAR. However, there may be rare occurrences when potential subjects are adequately oriented and lucid to be able to provide informed consent. Therefore, we will use a 2 step procedure (developed by Fan et al) to determine the patient's ability to provide informed consent. Step 1 is objective evaluation with the Richmond Agitation-Sedation Scale (RASS) and the Confusion Assessment Method for Intensive Care Unit (CAM-ICU). Patients who score -1, 0, +1 on the RASS indicating drowsy, alert, or restless respectively and are not delirious (CAM-ICU = No) will move to Step 2. Step 2 is assessment for competency using the MacArthur Competence Assessment Tool for Clinical Research: MacCAT-CR. This is the most widely used tool, and is the only tool that evaluates all four capacity domains (understanding, appreciation, reasoning, expression of a choice). Evaluation of Step 1 requires approximately 2-3 minutes, Step 2 requires approximately 15 minutes. Fan et al. found in consent evaluations of 150 ICU patients that 89% were sedated/delirious, and unable to provide consent; our experience in previous research is similar. Therefore, we expect that few potential subjects will move to Step 2. The LAR will then be contacted for those who fail Step 1 or Step 2. Subject's willingness to continue participation will be assessed on an ongoing basis throughout the project. We will follow the USF and TGH IRB Written Policies and Procedures, as well as the Florida regulations regarding appropriate use and definition of the LAR. The subject and the subject's LAR will be provided with an oral explanation of the nature of the study and study information, and information in writing, prior to seeking consent signatures. The information will include all elements required for informed consent, and will include all pertinent contact information as well as information about withdrawal from the study. Written documentation of consent will be obtained from the subject, if capable, or the LAR. If the potential subject or LAR does not wish to participate in the study, no additional interactions with the potential subject will take place. Further, subject's willingness to continue participation will be assessed on an ongoing basis throughout the project.

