
Once the subject has been enrolled, the Project Director will assign the subject to one of the three groups using a randomization schedule generated by [name]. A set of sequenced, sealed opaque envelopes will be prepared, each containing the assignment of an individual subject. At the time of enrollment, the Project Director will open the next envelope and proceed accordingly. [name] and the Data Manager will each keep a master copy of the randomization assignment.

Intervention and data collection procedures. Following obtainment of informed consent from the subject or LAR, subjects will be randomly assigned within 36 hours of intubation to one of three intervention groups which differ in frequency of tooth brushing (once, twice, or three times daily). The intervention, a standardized tooth brushing protocol developed and tested in the previous project, will be delivered by study personnel for 7 days, or until the subject is extubated if extubation occurs within the first 7 days.

Daily saliva periopaper GCF samples will be collected and digital images of teeth will be taken and identified only by the subject's arbitrary study number, not by any identifiable private information. GCF samples will be frozen at  $-70$  degrees in the Tampa General Hospital Office of Clinical Research Laboratory, and later transported to the

Biobehavioral Laboratory at the USF CON, and stored securely in the locked, limited access laboratory. Digital images of teeth will be obtained at close range such that photos will not include subject facial features.

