#### **L. CONSENT ISSUES**

##### **1. CONSENT PROCESS**

The Principal Investigator, Project Director or GRAs will recruit and enroll subjects. Study personnel will review each subject's medical record and confirm with the medical staff that the subject is age 18 or older and if there are no barriers to inclusion, the potential subject will be approached for enrollment. The subject's ability to participate in consent processes will be evaluated as previously described. The subject and the subject's legally authorized

representative (LAR) will be provided with an oral explanation of the nature of the study and study information in writing. In any instance where the potential subject's ability to comprehend and communicate his/her desires is in question, we will seek consent for continued participation from the LAR and will invite the research subject to provide his/her assent. Further, subject's willingness to continue participation will be assessed on an ongoing basis throughout the project. We will follow the USF and TGH IRB Policies and Procedures and Florida Code.

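### Single-site permuted blocks of apparently constant size, with every envelope opened by one of the recruiters, could let some assignments be deduced before enrolment if the block size is known or inferred

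*Combined protocol and SAP*

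**What the plan says.** Section IX (Sample) gives the method: "Subjects will be randomized to group according to a permuted block design", "such that after every $k$ subjects balance will be maintained between the groups". The symbol k has no value. Varying block sizes and stratification factors are not mentioned. The Setting paragraph places all recruitment and treatment at one hospital, so there is one assignment sequence.

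On who does what:

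- Screening (Procedures, Recruitment and enrollment): "The PI, co-investigators, Project Director or GRAs will make daily rounds to the adult ICUs".
- Recruiting (Section XVI.L.1): "The Principal Investigator, Project Director or GRAs will recruit and enroll subjects".
- Concealment (Procedures): "A set of sequenced, sealed opaque envelopes will be prepared, each containing the assignment of an individual subject".
- Allocation (Procedures): "At the time of enrollment, the Project Director will open the next envelope and proceed accordingly". The preceding text places this step after the subject has been enrolled.
- List holders (Procedures): the person who generated the schedule and "the Data Manager will each keep a master copy of the randomization assignment". The Project Director is not named as a holder.

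Section IX also says that the arms differ in how often study personnel brush the teeth each day, that outcome data are collected by blinded personnel, and that plaque is scored later from blinded images.

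**The concern.** Sealed opaque envelopes protect against reading the next card. They do not protect against working it out from earlier cards in the same block. A person who has seen every earlier assignment, and knows where a block ends, can name the last assignment in each block and sometimes more. Here the Project Director sees every assignment, and staff who deliver the brushing know the arm of each subject they treat.

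What is at stake is selection at entry: whom to approach, and when within the 36-hour window. The enrolment target is 10 per month, about one subject every three days, so a deduced slot could stay known for days. The arms also differ in staff burden. At about 15 minutes per session (Section IX, Intervention), they need roughly 15, 30 or 45 minutes of bedside time a day. Steering need not be deliberate.

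The analysis protects the two main comparisons unequally. The plaque ANCOVA adjusts for baseline plaque and timing of the assessment. The HAI proportions, incidence rates and number needed to harm (NNH) under Specific Aim 2 are unadjusted. Table 2 changes the recommendation at NNH 50 and 100 when non-inferiority is not supported. Read per subject (an assumption, since the plan's formula uses incidence rates), those cut-offs are differences of 2 and 1 percentage points. With 345/3 = 115 randomized per arm, one event is 1/115 = 0.87 points.

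**Working it through.** **The plan's own figure.** The documents give no figure for block size or predictability. The sample size, used here only as the length of the sequence, reproduces: n per group = 2(z₀.₉₀ + z₀.₉₅)²/0.50² = 2(1.2816 + 1.6449)²/0.25 = 68.5, rounded up to 69. Then 3 × 69 = 207, and 207/0.60 = 345.

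**Inputs.** Three equal arms and 345 assignments in one sequence (Sections IX and XI). Assumed: a constant block size k = 3m, with m places per arm; a recruiter who knows k and sees all past assignments; and k from 3 to 15, because no value is stated.

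**Share known with certainty.** An assignment is certain when only one arm has places left, that is, in the final same-arm run of the block. For a given arm, the 2m places of the other arms create 2m + 1 gaps, and on average m/(2m + 1) of that arm's places fall in the last gap. Summing over three arms gives 3m/(2m + 1) certain assignments per block. Dividing by 3m gives a share of 1/(2m + 1).

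**Best guess.** The recruiter names the arm with most places left. For k = 3 the success rate is (1/3 + 1/2 + 1)/3 = 61.1%. For k = 6, position by position, it is (1/3 + 2/5 + 1/2 + 8/15 + 3/5 + 1)/6 = 56.1%. Larger blocks were enumerated exactly in the same way.

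| k | Certain share | About, of 345 | Best guess right |
|---|---|---|---|
| 3 | 1/3 = 33.3% | 115 | 61.1% |
| 6 | 1/5 = 20.0% | 69 | 56.1% |
| 9 | 1/7 = 14.3% | 49 | 53.2% |
| 12 | 1/9 = 11.1% | 38 | 51.2% |
| 15 | 1/11 = 9.1% | 31 | 49.7% |

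Chance is 33.3%. At k = 6, at least one arm is already ruled out for 47% of assignments.

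**Effect of varying block sizes.** This was simulated with 200 sequences of 345. The guesser knows the set of sizes but not their order, and updates by Bayes' rule. As a check, the same program with fixed k = 6 gave 19.8% certain and 56.0% right, against the exact 20.0% and 56.1%.

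| Sizes in use | Certain share | Best guess right |
|---|---|---|
| 3, 6 | 8.7% | 57.8% |
| 3, 6, 9 | 3.8% | 55.4% |
| 6, 9, 12 | 2.4% | 52.9% |

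Varying the sizes removes most certainty but does little to the best guess. A recruiter who does not see past assignments is back at 33.3% whatever the block scheme.

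**The case against.** The strongest reply is that these percentages need a recruiter who knows k and tracks the sequence. The protocol does not print k, does not say recruiters are told it, and does not name the Project Director as a holder of the list. Leaving k unprinted may itself be a safeguard. This stands in part, and is why the figures are conditional. But the documents do not say that k is withheld, and a small constant k could be worked out by someone who opens every envelope.

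Nor do the words fixed block size appear. A single k is the plain reading of a short description that does not expressly exclude varying blocks.

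A reader might infer that one person screens, enrols and allocates every subject. The text does not say so. Several roles screen and recruit, so exposure depends on how many enrolments the Project Director handles or influences.

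Room for steering is also limited. All intubated ICU patients are to be assessed, Section XVI.B commits to recruiting every patient who meets the criteria, most criteria are objective, and imminent death is judged by the clinical provider. APACHE III is recorded, so an imbalance in severity would be visible. These points narrow the opening. They do not close it, because the order and timing of approaches remain with the study team and the HAI comparison is not adjusted for severity.

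**Conclusion.** The concern holds as a conditional weakness in allocation concealment. With one constant block size that a recruiter knows or infers, and all past assignments seen, between about 9% (k = 15) and 33% (k = 3) of assignments could be named before the envelope is opened. Best-guess success would be about 50% to 61%.

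Two stronger readings are tempting and are not supported. The first is that upcoming assignments as a whole are predictable: most are not certain at any k examined, and the condition on k is not established. The second is that the plaque and HAI results are biased: the documents show an opportunity, with no direction or size of bias. Blinded image scoring and blinded data collection mean that the issue lies at enrolment, not at assessment, and baseline adjustment gives the plaque comparison some protection. The sample size is unaffected.

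**What to change.** Two changes to Section IX (Sample) and Procedures:

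1. Separate recruitment from allocation. The Data Manager, who already holds the list, or another list holder who does not recruit, releases each assignment only after enrolment has been logged. As far as practical, those who decide whom to approach should not track past assignments. This is the more important element. It will be incomplete, because staff who deliver the brushing necessarily see the frequency.
2. Generate the list with randomly varying block sizes, for example 3, 6 and 9 or 6, 9 and 12, and state that the sizes are withheld from everyone who recruits. The text should not present this as sufficient alone, since it mainly removes the certain assignments.

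The cost is a regenerated list and a few sentences. The drawbacks are a slightly larger possible imbalance at the end of the trial and the need for the releasing person to be available within the 36-hour window.
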